### 2.2.1. Estimands

The estimand with treatment policy strategy will be utilized. All observed data (regardless of whether an intercurrent event occurs) will be included in the analysis. It includes the following 4 attributes:

- Population: Participants with COVID-19 pneumonia who meet all inclusion/exclusion criteria. The analysis will consider all observed data without employing any imputation for missing data;
- Variable: Yes or No for the occurrence of the event for categorical endpoints (including Binary endpoints), change from baseline for continuous endpoints and time to event for time to event endpoints.
- Intercurrent event(s): discontinuation of study intervention due to any reason or receiving rescue therapy.
- Population level summary: Proportion for categorical endpoints (including binary endpoints), mean for continuous endpoints and median time to event for time to event endpoints.

[figure not shown]
### 2.3. Study Design

The study concluded prematurely with a smaller-than-anticipated participant cohort, attributed to the return to pre-pandemic conditions as COVID-related restrictions eased during the recruitment phase. The situation warranted early termination of the study.

The study is a randomized, double blinded, placebo-controlled Phase 2b study of the efficacy and safety of tofacitinib in hospitalized adult (18-65 years old) male and female

patients with SARS-CoV-2 and pneumonia who require supplemental oxygen and have serologic markers of inflammation but do not need mechanical ventilation (see Inclusion criteria). Sixty patients will be recruited to receive tofacitinib or placebo in addition to standard of care (SOC) in a 2:1 ratio. Subjects will be screened during hospitalization. Patients with confirmed SARS-CoV-2 infection, and meeting all other Inclusion and Exclusion criteria, will be randomized to either treatment with tofacitinib or placebo in addition to SOC during hospitalization (dose adjusted, if required), with the exception of any immunomodulatory agents (as documented in the inclusion/exclusion criteria). Tofacitinib will be administered in a dose of 10 mg PO BID until return to their clinical baseline (as defined by need for supplementary oxygen) and will continue to be administered at 5 mg PO BID for a total duration of therapy of 14 days; follow-up off tofacitinib will continue up to Day 90. Because patients are likely to be discharged from the hospital soon after returning to clinical baseline, patients will continue to be administered tofacitinib 5 mg BID for a total duration of treatment of 14 days in order to prevent rebound of CRS that could theoretically occur with abrupt cessation of immunomodulatory therapy. In these cases, patients will be discharged home with a pill bottle labeled as investigational drug containing the appropriate number of pills (either tofacitinib or placebo). Rescue therapy is defined as IL-6 targeting agent or other non-FDA approved, compassionate use or expanded access when considered as medically necessary (AS REVIEWED BY THE PI) (Protocol section 6.1.2). Per protocol, subjects will discontinue from study treatment prior to taking rescue therapy.

**Figure 1. Study Schema**

### **3. ENDPOINTS AND BASELINE VARIABLES: DEFINITIONS AND CONVENTIONS**

#### **3.1. Primary Efficacy Endpoint(s)**

The primary objective is to determine whether tofacitinib improves the clinical outcomes of patients with moderate SARS-CoV-2 infection as determined by the primary outcome measure. The primary endpoint is proportion of subjects alive and not needing any form of mechanical ventilation, high flow oxygen, or ECMO by day 14.

#### **3.2. Secondary Efficacy Endpoint(s)**

- Clinical improvement (defined as a 2-point increase) as measured by NIAID 8-point ordinal scale (i.e., 1 = death and 8 = Not hospitalized, no limitations on activities) at day 14.
- Clinical status using ordinal scale (days 3 through day 14): The ordinal scale is an assessment of the clinical status at the first assessment of a given study day.
- Time to recovery [ Time Frame: Day 1 through Day 14] (Day of recovery is defined as the first day on which the subject satisfies one of the following three categories from the clinical status of ordinal scale: 6) Hospitalized, not requiring supplemental oxygen - no longer requires ongoing medical care; 7) Not hospitalized, limitation on activities and/or requiring home oxygen; 8) Not hospitalized, no limitations on activities.
- Time to clinical improvement (defined as a 2-point increase on the ordinal scale).
- Clinical status on ordinal scale at day 30, 60, and 90
- Mortality rate at day 30, 60, 90
- Proportion of patients requiring ICU admission and mechanical ventilatory support
- Change from baseline in inflammatory parameters hsCRP, procalcitonin, ferritin, D-dimers, LDH, fibrinogen, PT/PTT
- Change from baseline in cytokines IL-1, IL-2, IL-6, IL-8, TNF- $\alpha$ , IL-17A, IL-17F, IP-10, CCL5 as available.
- Intervention with additional immunomodulatory agent (i.e. IL-6 targeting therapy)
- Change in SARS-CoV-2 viral titers during intervention.

#### **3.3. Other Efficacy Endpoint(s)**

N/A

#### **3.4. Baseline Variables**

Unless specifically stated otherwise, the Baseline value is defined as the last non-missing measurement prior to the first administration of study drug at Day 1. As per protocol, it is intended all Day 1 assessments will be performed prior to dosing.

### 3.5. Safety Endpoints

#### 3.5.1. Adverse Events

An adverse event is considered a TEAE to a given treatment (for a participant who received at least of one dose of study intervention) if the event start date is on or after the treatment period start date and within 28 days of the treatment end date. The safety endpoints will be as follows.

- Incidence of TEAEs.
- Incidence of SAEs, and AEs leading to discontinuation.

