 - Known active tuberculosis or history of inadequately treated tuberculosis;
 - Known HBV, HCV, or HIV.

Prior/Concomitant Therapy:

Have received any of the following treatment regimens specified in the timeframes outlined below:

Within 4 weeks prior to the first dose of study intervention:

- Prior treatment with any JAK inhibitors, potent immunosuppressants, or any biologic agents including IL-6 inhibitors (eg, tocilizumab) or IL-1 inhibitors (eg, anakinra) within the past 28 days or 5 half-lives, whichever is longer.
- Prior treatment with any potent cytochrome P450 inducer, such as rifampin, within the past 28 days or 5 half-lives, whichever is longer.

Within 48 hours prior to the first dose of study intervention:

• Treatment with herbal supplements.

Received >/= 20 mg/day of prednisone or equivalent for >/=14 consecutive days in the 4 weeks prior to screening

Diagnostic Assessments:

- Severe hepatic impairment, defined as Child-Pugh class C.
- Severe anemia (hemoglobin <8 g/dL).
- ANY of the following abnormalities in clinical laboratory tests at screening, confirmed by a single repeat, if deemed necessary:
 - WBC <1000/mm3
 - Absolute lymphocyte count <500 cells/mm³;
 - Absolute neutrophil count <1000 cells/mm³.
- Alanine transaminase/aspartate transaminase (ALT/AST) > 5 times the upper limit of normal;
- Estimated glomerular filtration rate (eGFR) < 40 mL/min/1.73 m2);

Other Exclusions:

- Known allergy to tofacitinib.
- Investigator site staff or Pfizer employees directly involved in the conduct of the study, site staff otherwise supervised by the investigator, and their respective family members.
- Enrollment in another clinical trial to study COVID-19

Treatment Considerations

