6.1.8 Study Intervention Compliance

When the individual dose for a participant is prepared from a bulk supply, the preparation of the dose will be confirmed by a second qualified member of the study site staff.

When participants are dosed at the site, they will receive study intervention directly from the investigator or designee, under medical supervision. The date and time of each dose administered in the clinic will be recorded in the source documents and recorded in the CRF. The dose of study intervention and study participant identification will be confirmed at the time of dosing by a member of the study site staff other than the person administering the study intervention.

When compliance of less than 70% or more than 120% of the expected number of doses of study intervention is suspected, the reason for non-compliance with the dosing regimen should be documented in the dosing log of the participant's case report form, and should be reported as a protocol deviation and unless there is a protocol stipulated reason for non-compliance with the dosing regimen, this should be recorded as a dosing error.

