6.3 Study Procedures

6.3.1 Study Schedule

Visit Identifier ^{Error!} Reference source not found.	Screening	Day 1	Daily assessments (days 2-14) ^{c,d}	Early Termination/ Discontinuation/ End of Treatment (Day 14 or Discharge)	Follow-up ^{Erro} r! Reference source not found. (Dav 28)	Follow-up (Day 60)	Follow up (Day 90)	Early Termination/ Discontinuation
Visit Window	48 hours prior				+/-3 days			
	to Day 1							
Informed consent	х							-
Medical history	х							
Physical examination ^d	х	х	х	Х	Х			
Weight ^d	Х							
Vital signs ^d (pulse, blood pressure, respiratory rate ^e , temperature ^f)	Х	×		X	Х			
Laboratorv ^d			х					
Hematology	X		X		N N			
	X	X	Χ	X	X			
Blood chemistry	х	х	Х	Х	х			
Coagulation ^g	Х	х	х	Х	х			
Inflammation panel ^h	х	х	х	Х	Х			
Cardiac panel ⁱ	х	х	х	Х	х			
Pregnancy test	Х				Х			
Oxygen saturation by pulse oximetry (SaO ₂) ^d	Х	х	х	Х	Х			
12 Lead ECG ^d	Х	х	х	Х	Х			
Record if admitted to intensive care unit (ICU)	Х	х	х	Х	х			х
Registration/randomization		х						
Study drug administration		х	х	Х				
NIAIA Ordinal scale of disease severity	х	х	х	Х	х	х	х	х

APPROVED BY THE YALE UNIVERSITY IRB 9/28/2020

Protocol 2000027848

Version R5; 15 SEPTEMBER 2020

Visit IdentifierError! Reference source not found.	Screening	Day 1	Daily assessments (days 2-14) ^{c,d}	Early Termination/ Discontinuation/ End of Treatment (Day 14 or Discharge)	Follow-up ^{Erro} r! Reference source not found. (Day 28)	Follow-up (Day 60)	Follow up (Day 90)	Early Termination/ Discontinuation
Visit Window	48 hours prior				+/-3 days			
	to Day 1							
Record hospitalization status	х	х	х	Х	х	х	х	х
Assessment signs and symptoms of pneumonia		х		Х	х	х	х	
FiO2	х	х	х	х				
supplemental oxygen	х	х	х	х				
Blood for exploratory analysis ⁱ		х	Day 7	х	х			
Paxgene sample for exploratory biomarker analysis ^k		х	Day 7	х				
Plasma, Saliva and/or nasal swab for SARS-CoV-2 and exploratory analysis ^m		х	Day 7	х				
Whole blood for FACS analysis ⁿ		х	Day 7	х	x			
Concomitant treatment(s)		Х	Х	Х	X			Х
Adverse event monitoring	Х	Х	Х	Х	×	Х	Х	X□

Visit Identifier ^{Error! Reference source} not found.	Screening	Day 1	Daily assessments (days 2-14) ^{c,d}	Early Termination/ Discontinuation/ End of Treatment (Day 14	Follow-up ^{Erro} r! Reference source not found.	Follow-up (Day 60)	Follow up (Day 90)	Early Termination/ Discontinuation
Visit Window	48 hours prior to Day 1			or Discharge)	(Day 28) +/-3 days			

a. Day relative to start of study intervention (Day 1).

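### SAP 3.5.1 defines a TEAE by start date alone, so an AE recorded before dosing that worsens on study drug is left out of TEAE incidence unless re-entered as new, while a pre-dose Day 1 event is counted

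*SAP*

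**What the plan says.** SAP 3.5.1 applies its TEAE definition "for a participant who received at least of one dose of study intervention" and counts an event "if the event start date is on or after the treatment period start date and within 28 days of the treatment end date". Both limits are calendar dates applied to the start of the event. There is no clock time and no clause for a condition that began earlier and became worse. The start of the treatment period is not defined further. The footnotes to the schedule in Protocol 6.3.1 set Day 1 as the start of study intervention, so the first-dose date is the natural reading.

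SAP 3.4 uses a different cut for measurements: "the Baseline value is defined as the last non-missing measurement prior to the first administration of study drug at Day 1". It adds that "it is intended all Day 1 assessments will be performed prior to dosing".

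Protocol 6.3.1 schedules adverse event monitoring at screening, which may be up to 48 hours before Day 1, and again on Day 1. Protocol 5.3.2 admits participants with abnormal laboratory values short of its exclusion limits. For liver enzymes the exclusion is "Alanine transaminase/aspartate transaminase (ALT/AST) > 5 times the upper limit of normal". The other limits are lymphocytes below 500, neutrophils below 1000 and hemoglobin below 8 g/dL.

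**The concern.** Two kinds of event fall on the wrong side of the rule.

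- **Worsening on study drug.** An adverse event entered at screening keeps its screening start date. If it becomes more severe after dosing starts, it still fails the date test. Changes in blood counts, hemoglobin and liver enzymes are among the risks that Protocol 3.2.1 names for tofacitinib. In participants who already have abnormal values, a drug effect may appear as worsening rather than as a new onset. If worsening were more frequent on tofacitinib, the omission would fall mainly on that arm.
- **Events on Day 1 before the first dose.** These pass the date test although no drug has been taken. The same Day 1 laboratory abnormality could be the baseline value under SAP 3.4 and a treatment-emergent event under SAP 3.5.1.

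SAP 5.1 removes hypothesis testing, so no error rate is affected. The incidence by arm is itself what will be read.

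**Working it through.** The plan gives no figure to reproduce. The check applies the rule to test cases and then bounds the two effects.

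**Step 1. Classification.** Assume, for illustration, a first dose at 14:00 on Day 1 and a last dose on Day 14.

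| Event | SAP 3.5.1 as written | First-dose date-time cut plus worsening clause |
|---|---|---|
| Onset 09:00 on Day 1 | TEAE | not a TEAE |
| Onset 18:00 on Day 1 | TEAE | TEAE |
| Onset at screening, worse on Day 5 | not a TEAE | TEAE |
| Onset 28 days after last dose | TEAE | TEAE |
| Onset 29 days after last dose | not a TEAE | not a TEAE |

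Rows 1 and 3 change. The end of the window plays no part in either.

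**Step 2. Share of TEAEs that are pre-dose Day 1 events.** Inputs: a treatment course of 14 days (Protocol 6.1.2) and the limit "within 28 days of the treatment end date" (SAP 3.5.1), so the window is 14 + 28 = 42 days. Two assumptions are not in the documents: a constant event hazard over the window, and the clock hours of the first dose.

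Share = (mean first-dose hour / 24) / 42.

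| Assumed first-dose hours | Mean hour | Pre-dose part of Day 1 | Share of 42-day TEAEs |
|---|---|---|---|
| 08:00 to 12:00 | 10 | 10/24 = 0.42 | 1.0% |
| 10:00 to 20:00 | 15 | 15/24 = 0.62 | 1.5% |
| 16:00 to 22:00 | 19 | 19/24 = 0.79 | 1.9% |

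**Step 3. Effect of one participant.** SAP 7 reports 24 randomised. The split by arm is not given. Protocol 5.1 states 1:1 and SAP 2.3 states 2:1, so both are shown.

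- 12:12: 1/12 = 8.3 points in either arm.
- 16:8: 1/16 = 6.3 points in the larger arm, 1/8 = 12.5 points in the smaller.

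Incidence counts participants. Each figure therefore applies only if the reclassified participant has no other TEAE in the window.

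**Step 4. Frequency of worsening.** The documents give no adverse event counts, onset times or grade changes, so this part cannot be sized.

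**The case against.** A reader might infer that worsening of a pre-dose event disappears from the safety report. The documents do not support that. SAP 3.5.1 lists serious adverse events and events leading to discontinuation without a treatment-emergent limit. SAP 3.5.2 reports clinically significant laboratory abnormalities and change from baseline. Take ALT at 3 times the upper limit at screening and 6 times on Day 6. It meets a required discontinuation criterion in Protocol 6.1.2 and would be visible in those other summaries. Marked falls in lymphocytes, neutrophils or hemoglobin also have discontinuation thresholds there.

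The screening value might also never be entered as an adverse event. Protocol 6.2.3 ties the term to use of an intervention, so a site could treat the value as a baseline finding and enter the later rise as a new event, which would be a TEAE. This is possible, but neither document instructs it.

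Infection is a weaker example than laboratory values. Protocol 5.3.2 excludes active systemic infection other than COVID-19, so only a localised infection, or one missed or arising between screening and the first dose, could worsen in this way.

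Pre-dose Day 1 events should be balanced between arms, because allocation is randomised and blinded. A reader might also divide by the 14 treatment days alone and obtain 3.0% to 5.7%, but the rule's own window runs for 28 further days.

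Finally, dose times are available ("The date and time of each dose administered in the clinic will be recorded in the source documents and recorded in the CRF"), but no section says that onset times of adverse events are collected. Without them, a time-of-day cut changes nothing on Day 1.

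All of this limits the size of the point. None of it supplies a worsening rule for the TEAE table.

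**Conclusion.** The point holds and is minor. Followed as written, SAP 3.5.1 leaves out of TEAE incidence an event recorded before dosing that worsens on study drug, unless the site re-enters it. It also counts pre-dose events on Day 1, which is inconsistent with the cut in SAP 3.4. No other section corrects either result. The omission of worsening is the more important of the two, because it need not be balanced between arms.

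The effect is confined to one table, and much of any marked worsening would appear elsewhere in the safety output. The 1.0% to 1.9% share for Day 1 rests on the assumed hazard and dosing hours. The shifts of 6.3 to 12.5 points are conditional on a single reclassified participant with no other TEAE. The conclusion also reads the start of the treatment period as the date of the first dose.

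**What to change.** Reword SAP 3.5.1 so that an adverse event is treatment-emergent in either of two cases, keeping the present end of the window:

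- it starts at or after the first dose, using the onset time on Day 1 where recorded and otherwise counting a Day 1 event as emergent; or
- it began before the first dose and increased in severity or became serious at or after it.

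List adverse events with onset before the first dose separately.

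The cost is one SAP sentence, one programming change and one listing. Where onset time or change of grade was not recorded, a few events among 24 participants will need a chart check. If Day 1 onset times were not collected, the default keeps the present classification for those events and the worsening clause is the part that has effect.

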#### 3.5.2. Laboratory data

The following laboratory tests will be performed at time points identified in the Schedule of Activities. Unscheduled clinical labs may be obtained at any time during the study to assess any perceived safety concerns at the investigator's discretion or Sponsor's request.

- Blood and urine laboratory tests including lactate dehydrogenase (LDH), complete blood count with differential (CBC), comprehensive metabolic panel (CMP), cytokine panel, cardiac panel, coagulation, inflammation panel, and urinalysis.

The following endpoints for laboratory data will be analyzed.

- Incidence of clinically significant abnormalities in laboratory parameters
- Changes in Clinical laboratory parameters from the baseline (hemoglobin, hepatic transaminases, serum creatinine, bilirubin, and evidence of secondary infections).

#### 3.5.3. Vital signs

Vital signs (pulse, blood pressure, respiratory rate, temperature) will be measured as indicated in the Schedule of Activities of the protocol. The following endpoint will be analyzed: incidence of clinically significant abnormalities in vital signs.

#### 3.5.4. Electrocardiogram (ECG)

ECGs should be collected at times specified in the Schedule of Activities of the protocol. The following endpoints will be analyzed:

- Changes from baseline for the ECG parameters

### 4. ANALYSIS SETS (POPULATIONS FOR ANALYSIS)

Population	Description	Applicable Analysis
Full analysis set (FAS)	All participants randomly assigned to study intervention. Participants will be analyzed according to the	All efficacy endpoints

	intervention to which they were randomized.	
Safety analysis set (SAS)	All participants randomly assigned to study intervention and who take at least 1 dose of study intervention. Participants will be analyzed according to the intervention to which they received.	All safety endpoints

If a participant is randomized but receives the incorrect treatment, then the participant will be reported under the randomized treatment group for all efficacy analyses. If a participant is randomized but receives partially incorrect treatment, then the participant will be summarized under the treatment received for most of the time during the study, for all safety analyses.

**5. GENERAL METHODOLOGY AND CONVENTIONS**

Final analyses will occur after database lock after LSLV.

**5.1. Hypotheses and Decision Rules**

No Hypotheses testing.

**5.2. General Methods**

**5.2.1. Analyses for Categorical (including Binary) Endpoints**

Categorical (including binary) data will be analyzed using the Estimand with treatment policy strategy specified in Section 2.2.1. All summary statistics are based on each treatment group.

- The number of participants, number, and percent of participant with event along with the 95% confidence interval by Clopper-Pearson exact method (see reference in Section 8) will be presented for observed data.
- For Binary data over time, line plot for the event rate and 95% CI will be presented.

**5.2.2. Analyses for Continuous Endpoints**

Continuous endpoints will be analyzed using the Estimand with treatment policy strategy specified in Section 2.2.1.

The data for each continuous endpoint will be summarized by treatment group and by time point in tables containing descriptive statistics (N [which is the number of participants evaluable for the endpoint at the time point], mean, standard deviation, standard error of the mean, minimum, 1st, 2nd (i.e., median) and 3rd quartiles and maximum) for actual and change from baseline values for those endpoints measured at baseline. In case when N=1 (i.e., only one participant is available/evaluable for summary), standard deviation and standard error will be reported as “NA” (not applicable) while the remaining statistical parameters will

have the same value as the mean. For selected endpoints, mean (+/-SD) over time by treatment group will be plotted.

### **5.2.3. Analyses for Time-to-Event Endpoints**

For time to recovery and time to clinical improvement

- If subject died prior to or on the specified time point (Day 14 or Day 30), the result for time to event will be censored on the date of death regardless of if subjects have experienced recovery or clinical improvement prior to Death.
- If no death is recorded through the specified time point (Day 14 or Day 30): For a participant who experiences the event of recovery/clinical improvement through Day 14 or Day 30, the time to event will be the study day corresponding to the earliest visit date at which the participant has already experienced the event.
- For all participants who have not experienced the event, their time to event will be right censored at the last available measurement time of the clinical status through Day 14 or Day 30.

Time to event endpoints will be analyzed using the Estimand with treatment policy strategy specified in Section 2.2.1.

The number of participants, number and percent of participants censored, and participants with recovery or clinical response will be provided for each treatment group. The median and quartiles time to event will be estimated by the Kaplan-Meier method.

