6.5.2 Secondary Objectives Analyses

For the ordinal scale of disease severity, the proportion of patients in each category will be summarized by treatment group. A proportional odds model will be fit to compare tofacitinib

plus SOC versus placebo plus SOC. The odds ratio will be estimated along with its 90% confidence interval.

Endpoints such as time to recovery and time to improvement will be summarized with Kaplan Meier estimation and compared used log-rank tests. Cox proportional hazard model will be used to estimate hazard ratios.

For the binary outcomes, such as mortality rate at days 30, 60, and patients requiring ICU admission and mechanical ventilatory support, the analysis methods will be the same as for the primary endpoint.

For endpoints such as duration of invasive mechanical ventilation, invasive mechanical ventilation free days, death is a competing event, i.e if a patient dies before invasive mechanical ventilation, the duration of ventilation is unknown. This will be analyzed using competing risk model proposed by Andersen and Gill (1982). Generalized cox model will be used to estimate the hazard ratio for the treatment effect.

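### SAP 5.2.3 censors deaths without recovery at the death date and then uses Kaplan-Meier, so the quartiles and median of time to recovery or improvement can come too early, or exist when fewer than half recovered

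*SAP*

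**What the plan says.** SAP 5.2.3 covers the SAP's only two time-to-event endpoints, time to recovery and time to clinical improvement, over a Day 14 or Day 30 window. For anyone who dies within the window, "the result for time to event will be censored on the date of death". This applies "regardless of if subjects have experienced recovery or clinical improvement prior to Death", so it covers deaths with and without a prior recovery. For everyone else still event-free, "their time to event will be right censored at the last available measurement time of the clinical status through Day 14 or Day 30". The estimator is then fixed: "The median and quartiles time to event will be estimated by the Kaplan-Meier method".

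SAP 2.2.1 names "median time to event for time to event endpoints" as the population-level summary. It adopts a treatment policy strategy and lists treatment discontinuation and rescue as intercurrent events. Death is not listed.

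Protocol 6.5.2 says "Endpoints such as time to recovery and time to improvement will be summarized with Kaplan Meier estimation". For ventilation-duration endpoints the same section says "death is a competing event", but it does not extend this to recovery or improvement. Protocol 6.5.10 describes censoring for completion without the event and for withdrawal, and does not mention death.

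**The concern.** Kaplan-Meier treats a censored participant as someone who would go on to have the event at the rate of those still under observation. That is reasonable for a participant lost to follow-up. It is not reasonable for one who has died, because recovery is then impossible.

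The rule also ranks outcomes the wrong way round. A living participant who is still ventilated and followed to the end of the window stays in the denominator and holds the recovery curve down. A participant who dies unrecovered on Day 3 is removed from the denominator and lets the curve rise. The ordinal scale puts death lowest, yet in this analysis the death does less harm to the arm's recovery summary than prolonged ventilation.

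The median is the named summary and no test accompanies it, so it is the figure that readers will compare between arms. With identical recoveries, the arm with more early unrecovered deaths can show an earlier quartile or median.

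**Working it through.** The documents give no figure for time to recovery, so there is none to reproduce. The check asks what the rule does to the planned outputs.

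**Inputs.** From the documents: the censoring rule and estimator (SAP 5.2.3) and 24 randomized (SAP 7). Under the 1:1 ratio of Protocol 5.1 this is about 12 per arm; under the 2:1 ratio of SAP 2.3 it is about 16 and 8. Assumed: all recovery days, death days and death counts. Survivors without recovery are followed to Day 14.

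**Formula.** Under the SAP rule the estimated recovery by day *t* is 1 − Π(1 − d/n) over recovery days up to *t*, where d is recoveries and n is the number at risk after removing earlier deaths. If k of N recover and m die unrecovered before the first recovery, this reduces to k/(N − m). With death as a competing event and no other early censoring it is k/N. The median is taken as the first day on which the curve reaches 50%.

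**Example A: N = 12, recoveries on Days 4, 6, 8, 10, 12; deaths drawn from Days 3, 5, 7, 9.**
- No deaths: 5/12 = 41.7%; median not reached.
- Deaths on Days 3, 5: 1 − (10/11 × 8/9 × 7/8 × 6/7 × 5/6) = 49.5%; median not reached. Any one or two of the four deaths give 43.8% to 49.5%.
- Deaths on Days 3, 5, 7: 1 − (10/11 × 8/9 × 6/7 × 5/6 × 4/5) = 53.8%; median Day 12. Any three of the four give 51.9% to 53.8%, all with median Day 12.
- All four: 1 − (10/11 × 8/9 × 6/7 × 4/5 × 3/4) = 58.4%; median Day 12.
- Competing-risk estimate in every case: 5/12 = 41.7%; median not reached.

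**Example B: N = 12, recoveries on Days 5, 7, 9, 11, 13; deaths on Day 2.**
- One death: 5/11 = 45.5%; median not reached.
- Two deaths: 5/10 = 50.0%; the curve just reaches 50% and the median is Day 13.
- Three deaths: 5/9 = 55.6%; median Day 13.
- Competing-risk estimate throughout: 41.7%; median not reached.

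**Other arm sizes, two early unrecovered deaths.** 3 of 8 recovered: 3/8 = 37.5% becomes 3/6 = 50.0%. 7 of 16 recovered: 7/16 = 43.8% becomes 7/14 = 50.0%. In both a median appears where there was none.

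**Where most recover: N = 12, recoveries daily on Days 3 to 10 (8/12 = 66.7%).** Deaths on Day 2 and between Days 5 and 6 leave the median at Day 8. The curve ends at 1 − (10/11 × 9/10 × 8/9 × 6/7 × 5/6 × 4/5 × 3/4 × 2/3) = 79.2%, so an upper quartile of Day 10 is reported although fewer than 75% recovered. A third death, between Days 3 and 4, moves the median to Day 7.

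**Limits on direction.**
- Deaths after the last recovery: N = 12, recoveries on Days 5, 7, 9, 11, deaths on Days 12, 13. The estimate is 4/12 = 33.3% under either method.
- Recovered, then died: in Example B without early deaths, suppose the Day 5 recoverer dies on Day 10. The SAP rule gives 1 − (11/12 × 10/11 × 8/9 × 7/8) = 35.2% instead of 41.7%. The same sentence here pushes the other way.

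**The case against.** The strongest reply is that little of the plan rests on this number. SAP 5.1 has no hypothesis testing, these are secondary endpoints, and the primary endpoint counts death as failure. Mortality at Days 30, 60 and 90, and ordinal status with death as its lowest category, are reported separately. All of that stands and lowers the severity. It does not make the median right: 5 of 12 recovered could sit in the same table as a median of Day 12.

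A reader might infer that the trial will report an inflated recovery percentage, such as 58.4% instead of 41.7%. The SAP does not support that. It takes only the median and quartiles from Kaplan-Meier and reports the number with recovery directly, so 5 of 12 would be shown either way. The percentages above only explain why the quartiles move.

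A reader might also infer that every early death flatters its arm. That is too broad. The effect needs a death without recovery followed by a later recovery in the same arm, and a recovery followed by death works in the opposite direction. Nor can one say that either arm is favoured in fact, because no death count is given. Eligibility excludes mechanical ventilation or ECMO at randomization and anticipated survival under 72 hours, so deaths may be few. With one or two deaths in Example A, no median appears.

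Finally, the protocol also planned Kaplan-Meier. That is true, but it did not say to censor at the date of death; SAP 5.2.3 added that step.

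**Conclusion.** The rule is wrong as written and nothing else in the SAP corrects it. Unrecovered deaths that precede a later recovery bias the reported quartiles and median early and can produce a median when fewer than half the arm recovered. With arms of about 8 to 16, two such deaths can be enough when recovery is just under one half; in Example A it takes three of 12, and where most participants recover the median moves less readily. These sizes rest on assumed event days and death counts, so the actual effect is unknown and could be nil. Because the analysis is descriptive and the endpoints are secondary, this is a should-fix.

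**What to change.** In SAP 5.2.3, replace the death bullet with a rule that covers both cases:
- Death in the window without prior recovery or improvement is a competing event. Read the median and quartiles, or not reached, from the Aalen-Johansen cumulative incidence curve, for both the Day 14 and the Day 30 window.
- A recovery or improvement observed before death counts as an event on its own date.

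The two parts should be changed together, since correcting one alone leaves the other error standing.

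Holding unrecovered deaths as non-events to the end of the window is simpler, but matches Aalen-Johansen only when no one else is censored early. With Example A's recoveries, deaths on Days 3 and 5 and losses to follow-up on Days 7 and 9, holding gives 1 − (11/12 × 10/11 × 8/9 × 6/7 × 5/6) = 47.1%. Aalen-Johansen gives 1/12 + 1/12 + 0.0952 + 0.1143 + 0.1143 = 49.0%. Because SAP 5.2.3 allows censoring at the last available status, Aalen-Johansen is the safer choice.

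The cost is a short SAP edit and a standard procedure, with no new data. The downside is that an arm with unrecovered deaths will show a less favourable recovery summary.
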